4.7 Study Costs

The study will pay for visits that are done just for the research study. The participant or their insurance company will not be responsible for the cost of visits done just for the research study. The study will not pay for usual care visits. Usual care visits are those that would occur whether or not the subject is in the study. The cost of usual care visits will the responsibility of the participant or their insurance company.

- The study will pay for the 8-week study visit, as it is done just for the research study. Neither the participant or their insurance company will be responsible for the cost of the 8-week study visit.
- The study will pay for the participant's study glasses.

The study will not pay for contact lenses, tinted lenses, or antireflective coating.

4.8 General Considerations

The study is being conducted in compliance with the policies described in the study policies document, with the ethical principles that have their origin in the Declaration of Helsinki, with the protocol described herein, and with the standards of Good Clinical Practice.

Data will be directly collected in electronic CRFs, which will be considered the source data.

There is no restriction on the number of subjects to be enrolled by each site towards the overall recruitment goal.

- 1118 A risk-based monitoring approach will be followed, consistent with the FDA "Guidance for
- 1119 Industry Oversight of Clinical Investigations A Risk-Based Approach to Monitoring" (August
- 1120 2013).

1121 CHAPTER 5 SAMPLE SIZE ESTIMATION AND STATISTICAL ANALYSIS

1123 The sample size and statistical analyses are summarized below.

1124 1125

1122

The data collected in this short-term, pilot randomized trial will primarily be used to obtain preliminary estimates of treatment effect in both the prism and non-prism group to determine whether to proceed to a full-scale, longer-term randomized trial of prism vs. non-prism.

1127 1128 1129

1130

1131

1132

1126

5.1 Sample Size

Because this study is a pilot study, sample size has not been statistically calculated. The sample size of 64 participants (32 participants per group) who pass the prism adaptation test (i.e., do not fully prism adapt) is a convenience sample that is expected to provide at least 60 participants (30 participants per group) for analysis after adjusting for up to 5% loss to follow-up.

1133 1134 1135

The primary analysis section (section 5.2) indicates the level of statistical power/precision that the sample size of 30 participants per group (60 total) provides.

1136 1137 1138

1139

1140

Primary Analysis 5.2

The primary analysis will be an intent-to-treat comparison of mean 8-week control of the distance exodeviation (average of 3 measurements) between treatment groups using an analysis of covariance (ANCOVA) model, which adjusts for baseline distance control.

1141 1142 1143

1144

1145

1146

1147

5.2.1 Decision Guideline for Determining Whether to Proceed to a Randomized Trial

The data collected in this short-term, pilot randomized trial will primarily be used to determine whether to proceed to a full-scale, longer-term randomized trial of prism vs. non-prism. A decision guideline has been developed to aid in this decision (see below). The side effect profiles in each treatment group will also be considered when deciding whether to proceed with a full-scale trial.

1148 1149 1150

1151

1152 1153

1154

1155

1156

1157

The decision guideline for determining whether to proceed to a full-scale randomized trial will be based on the primary analysis estimate of the treatment group difference in mean distance control scores at 8 weeks. The standard deviation of 8-week distance control in IXT3 was 1.5 points (95% CI = 1.2 to 1.8 points). The convenience sample of 64 participants yields relatively low statistical power (61%) for detecting a difference if the true difference = -0.75 assuming an SD in the current study of 1.5 points and accounting for up to 5% loss to follow up. As the statistical power is poor, the decision guideline was based solely on the size of the observed difference in mean control scores (prism – non-prism). The decision is:

- **Proceed** if the observed difference < -0.75 points 1158
- 1159 • Uncertain if the observed difference favors the prism group by less than 0.75 points (diff <0 1160 and > -0.75)
- 1161 • **Do not proceed** if the observed difference is zero or favors the non-prism group (diff ≥ 0)

1162 1163 1164

*Note that differences (prism – non-prism) favoring prism will be negative given that lower control scores indicate better control.

1165 1166

1170

1171 1172

1173 1174

1175 1176

1177 1178

1179 1180 1181

1182 1183

1184

1185

1186 1187

1188

1189

1190

1191 1192

1193 1194 1195

1196 1197

1201

Decision Guideline #1: Whether to Proceed to	TRUI	(Prisn	nent Gro 1 – Non- in point	. ,	erence
Full-Scale Randomized Trial Based on OBSERVED Difference in Means in Pilot Study	-0.25	-0.50	-0.75	-1.0	-1.25
Proceed** if observed difference is ≤-≤0.75	11%	27%	50%	73%	89%
Uncertain if observed difference is <0 and > -0.75	62%	62%	46%	26%	11%
Do not proceed if observed difference is ≥0	27%	11%	4%	1%	0%

- Table cells show the probability of making the given decision if the true difference is the given amount. Estimates were calculated using a 1-sided t-test, a standard deviation of 1.5 and 30 participants per treatment group.
- ** The 'proceed' row is the chance of observing a difference of 0.75 points or larger favoring prism given varying assumptions for the true treatment difference.

As seen in Table 1, the probability of making a 'proceed' decision when the true mean difference is -0.75 points or larger is 50%, the probability of an 'uncertain' decision is 46%, and the probability of a 'do not proceed' decision is 4%. Even if the true mean difference is as small as -0.50 points, the probability of a "do not proceed" decision is still low at 11%.

5.3 **Secondary Analysis -- Distance Control**

The secondary analysis will calculate the proportion (and two-sided 95% confidence interval) of participants with a "treatment response," defined as ≥1 point improvement in control of their distance exodeviation (average of 3 measurements) between baseline and the 8-week outcome exam

5.4 Secondary Analysis – No Spontaneous Tropia

The proportion of participants with no spontaneous tropia at 8 weeks will be compared between treatment groups using a two-sided Barnard's test with alpha of 0.05, with calculation of a twosided 95% confidence interval on the difference in proportions.

No spontaneous tropia at the 8-week primary outcome exam is defined as a score of ≤ 2 (0, 1, or 2) on all three assessments of control at distance and at near.

5.5 **Additional Analyses**

5.5.1 Change in Distance Control

1198 In addition to the primary analysis comparing mean change in distance control between 1199 treatment groups (see section 5.2), the distribution of change in distance control will also be 1200 compared between treatment groups using the Wilcoxon rank sum test.

- 1202 5.5.2 Near Control
- 1203 Near control will be evaluated similarly to the distance control in the primary analysis (section
- 5.2), secondary analyses (section 5.3, 5.4), and one of the additional analyses (section 5.5.1). 1204

1205 5.5.3 Ocular Alignment

- 1206 The distribution of measures of ocular alignment at distance and near fixation by PACT will be
- 1207 described for the enrollment exam and the outcome exam for each treatment group. Because
- 1208 participants in the prism group will have PACT measured at 8-weeks while wearing study-
- 1209 prescribed relieving prism, we will account for this in analysis by adding the magnitude of the
- 1210 prescribed prism to the deviation by PACT while wearing prism for analysis of the total
- 1211 underlying deviation. We acknowledge this has limitations as measurement through ground in
- 1212 prism is not equivalent to measurement without ground in prism. The distribution of change in
- 1213 ocular alignment will also be described for each treatment group.

1214

1215 5.5.4 Near Stereoacuity

- 1216 The distribution of near stereoacuity will be described for the enrollment exam and the outcome
- exam for each treatment group. The distribution of change in near stereoacuity will also be 1217
- 1218 described for each treatment group.

1219

1220 5.5.5 Suppression

- 1221 As an exploratory analysis, the distribution of suppression level (none, mild, moderate, severe)
- 1222 will be described for the enrollment exam and the outcome exam for each treatment group.

1223 1224

5.5.6 Fusional Convergence

- 1225 As an exploratory analysis, the distribution of fusional convergence amplitude (break point, blur
- 1226 point, and recovery) will be described, and compared between treatment groups for the
- 1227 enrollment exam and the outcome exam for each treatment group.

1228 1229

5.5.7 Adverse Symptoms of Intermittent Exotropia and Prism Spectacle Wear

- 1230 Adverse symptoms of IXT will be assessed at enrollment and at the 8-week outcome exam using
- 1231 a symptom survey that is administered to the child (see section 2.4). Response options are based
- 1232 on frequency of observations: never, sometimes, and always.

1233

- 1234 Similarly, adverse symptoms that may be associated with prism spectacle wear will be assessed
- at enrollment and at the 8-week outcome exam using a spectacle survey that is administered to 1235
- 1236 the parent. Response options are based on frequency of observations: never, rarely, sometimes,
- often, always, and not applicable. 1237

1238

- 1239 For each survey separately, the distribution of scores on each survey item will be described for
- 1240 the enrollment exam and the outcome exam for each treatment group.

1241 1242

5.5.8 Distance Visual Acuity

- 1243 Distance visual acuity will be assessed at enrollment and at the 8-week outcome exam. Any
- 1244 optotype method can be used for testing; however, the same method must be used at both the
- 1245 enrollment and 8-week outcome exam.

1247 The distribution of distance visual acuity measures will be described for the enrollment exam and

1248 the outcome exam for each treatment group. The distribution of change in visual acuity will also

1249 be described for each treatment group.

1250 1251

5.5.9 Compliance of Spectacle Wear

1252 Parents will be asked to complete a compliance calendar by recording the percentage of time

- 1253 their child has worn the study-prescribed spectacle correction each day. Proportion of time worn
- 1254 each day will be described as excellent (76% to 100%), good (51% to 75%), fair (26% to 50%),
- 1255 poor (1 to 25%), or none (0%). Based on review of the calendars and discussion with parents at
- 1256 the 8-week outcome exam, the investigator will record the total proportion of time worn as
- 1257 excellent (76% to 100%), good (51% to 75%), fair (26% to 50%), poor (1 to 25%), or none (0%:
- 1258 did not fill prescription or never picked up spectacles).

1259 1260

The distribution of compliance will be assessed for each treatment group at the outcome exam.

1261 1262

1263

1264

5.5.10 Alternative Approach to Primary Analysis

A planned secondary analysis will be to repeat the primary analysis (see section 5.2) but limit it

to participants who received their study spectacles in sufficient time to allow for the opportunity

to have worn the spectacles for at least 4 weeks.

1265 1266 1267

5.5.11 Mean Distance Control in Subgroups

1268 As an exploratory analysis, the mean distance control score in subgroups based on baseline

- 1269 distance control severity will be estimated. The hypothesis for a subgroup effect based on
- 1270 distance control severity (2 to <3, 3 to <4, 4 to 5) is that poorer control is associated with larger
- treatment effect as suggested in a pilot study of overminus spectacles, ²³ another form of non-1271
- surgical IXT treatment. Although the greater magnitude of response with poorer baseline control 1272
- 1273 may have been at least partly attributable to regression to the mean and having more room for
- 1274 improvement, the same magnitude of response was not seen in the observation group, suggesting
- 1275 that the larger treatment effect with poorer baseline control observed when treating with
- overminus spectacles could be real.²³ 1276

1277 1278

1279

1280

These planned subgroup analyses will repeat the primary analysis, adding the baseline factor and the baseline factor by treatment interaction. It is acknowledged that these analyses have very low

power and only very strong interactions will be able to be detected. Any observed subgroup

1281 effects will require confirmation in a full-scale trial to be considered true effects.

1282 1283

5.5.12 Masking Assessment

1284 At the 8-week visit, the proportion of masked examiners who responded that the patient appears

- 1285 to be wearing prism glasses will be compared between treatment groups using a two-sided
- 1286 Barnard's test with alpha of 0.05, with calculation of a two-sided 95% confidence interval on the
- 1287 difference in proportions.

1288 1289

INTERMITTENT EXOTROPIA STUDY 6

Revision History

	RSION IMBER	AUTHOR	APPROVER	EFFECTIVE DATE	REVISION DESCRIPTION (INCLUDING SECTIONS REVISED)
SAP	Protocol				
1.0	V1.0	[name] [name]	[name]	4-15-20	Initial version

(IXT6)

A Pilot Randomized Clinical Trial of Base-in Prism

Spectacles for Intermittent Exotropia

STATISTICAL ANALYSIS PLAN

Version 1.0

March 4, 2020

Based on Protocol version 1.0 (May 29, 2019)

1. Objective of IXT6 Pilot Study

The objective of this short-term, pilot randomized trial comparing spectacles with relieving prism to spectacles without prism is to determine whether to proceed to a full-scale, longer-term randomized trial. This decision will be based primarily on assessing the initial (8-week) response to prism and the preliminary estimates of treatment effect in both the prism and non-prism group.

28 29 30

31

32

33

34

22

23

24

25

2627

2. Primary Analysis – Comparison of Control of Distance Exodeviation Between Treatment Groups

The primary analysis will be an intent-to-treat comparison of mean 8-week control of the distance exodeviation (average of 3 measurements) between treatment groups using an analysis of covariance (ANCOVA) model, which adjusts for baseline distance control [1].

353637

38

3940

41

42 43

44

45

46

47 48

49

50

51

52

Distance control at the 8-week visit (average of up to 3 measurements) will be tabulated by treatment group into the following categories: 0 to <1, 1 to <2, 2 to <3, 3 to <4, 4 to <5, and 5 points. The mean treatment group difference (prism – non-prism) and corresponding one-sided 95% confidence interval and p-value will be calculated. Although a two-sided test would be used in the longer-term, full-scale trial, a one-sided test is being used for the pilot study given that the decision whether to proceed to a fullscale trial is based only on whether overminus is better than the non-overminus control group. Model assumptions for the ANCOVA will be assessed, including linearity of the relationship with baseline distance control, normal distribution and equal variance across the treatment groups. If the linearity assumption is not met, a transformation for linearity will be performed, or baseline control will be categorized. Serious deviation of the mean 8-week control scores distribution from normality, conditional on treatment group and baseline control, is not expected given the outcome scale is bounded; but, if such deviation is observed, the van der Waerden normal scores transformation will be considered. An ANCOVA that allows for unequal variance in the 2 treatment groups will be used if the variance of the active treatment group differs from that of the control group by more than 20% [2].

535455

56

57 58

59

60

61 62 When the protocol-specified three measures of control are not performed at the outcome exam, the mean of two tests will be used for analysis if only 2 distance control tests are completed. The single distance control score will be used for analysis if only 1 testing is completed. To account for missing data, a record for each randomized participant will be included in the analysis dataset containing all independent variables in the ANCOVA model along with outcome data when available, and maximum likelihood-based estimation will be used to obtain an estimate of treatment effect. The estimate from this model is unbiased when there are missing outcome data, as long as those data are missing at random.

63 64 65

66

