1.14 Study Objective

The objective of this short-term, pilot randomized trial comparing spectacles with relieving prism to spectacles without prism is to determine whether to proceed to a full-scale, longer-term randomized trial. This decision will be based primarily on assessing the initial (8-week) response to prism by comparing treatment groups on the following outcomes:

- Mean distance IXT control score (the mean of 3 control scores) (primary outcome)
- The proportion of participants demonstrating a "treatment response," defined as ≥1 point improvement in the mean distance IXT control score without spontaneous exotropia during control testing (secondary outcome)
- The proportion of participants reporting adverse effects and good/excellent spectacle wear compliance

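### Does the overminus sentence in SAP section 2 give the pilot a different rule for proceeding to a full-scale trial?

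*SAP*

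**What the plan says.** SAP section 2 plans an ANCOVA of mean 8-week distance control, adjusted for baseline control. It defines the treatment difference as prism minus non-prism and reports a one-sided 95% confidence interval and p-value. It then explains the sidedness: a full-scale trial would use a two-sided test, but the pilot does not, because "the decision whether to proceed to a fullscale trial is based only on whether overminus is better than the non-overminus control group".

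The protocol describes the decision in three places.

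- **Section 1.14** bases it primarily on the 8-week response to "prism by comparing treatment groups on the following outcomes": mean distance control, treatment response, and "The proportion of participants reporting adverse effects and good/excellent spectacle wear compliance".
- **The preamble to Chapter 5** says the data serve mainly to give preliminary effect estimates in the two groups, from which the decision is to be made.
- **Section 5.2.1** offers a guideline as an aid. Because power is poor, "the decision guideline was based solely on the size of the observed" difference in mean control scores. There are three zones: Proceed at about -0.75 points or beyond, "Uncertain if observed difference is <0 and > -0.75", and Do not proceed at 0 or above. In addition, "side effect profiles in each treatment group will also be considered".

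SAP section 1 says the decision rests primarily on the 8-week response to prism and on preliminary estimates in both groups. The SAP does not restate the guideline or its cut-offs.

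**The concern.** Two things look wrong in one sentence. First, it names a treatment that nobody in this trial receives. Elsewhere in the two documents overminus appears as a treatment in earlier studies, as one of several non-surgical options, or as an exclusion or spectacle limit.

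Second, putting prism in its place does not seem to repair it. On a literal reading, direction alone decides. That conflicts with the size cut-offs and Uncertain zone of Protocol 5.2.1, with the stated role of side effects, and with the list of outcomes in Protocol 1.14.

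Whether to proceed is the pilot's declared purpose. If someone took the SAP sentence as the rule, a result that merely favoured prism, or that reached one-sided p<0.05, could be reported as supporting a full-scale trial when the guideline says Uncertain.

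A smaller worry is attached. SAP section 2 allows a van der Waerden normal scores transformation, whose estimate would not be in points and could not be set against -0.75.

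**Working it through.** **1. Is the analysed contrast affected?** No. The contrast is set out earlier in the same SAP paragraph as prism minus non-prism, and Protocol 2.8 randomizes to those two groups. No variable, model term or estimate depends on the word overminus.

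**2. Does the one-sided test agree with the protocol?** The inputs come from Protocol 5.2.1: difference 0.75, SD 1.5, 30 per group. The table footnote adds "Estimates were calculated using a 1-sided t-test".

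- SE = 1.5 × √(2/30) = 0.387, and 0.75/0.387 = 1.936.
- One-sided 0.05: Φ(1.936 − 1.645) = 61.5%. The noncentral t with 58 df gives 60.6%. The stated power is 61%.
- Two-sided 0.05: 49.1% (normal) or 47.8% (t), which does not match.

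The protocol's power is therefore a one-sided figure, and the SAP's choice agrees with it whatever reason the sentence gives.

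**3. Does the protocol's decision table reproduce?** With the same SE and a normal distribution for the observed difference:

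| True difference | Proceed / Uncertain / Do not proceed, recomputed | Stated |
|---|---|---|
| -0.25 | 10 / 64 / 26% | 11 / 62 / 27% |
| -0.50 | 26 / 64 / 10% | 27 / 62 / 11% |
| -0.75 | 50 / 47 / 3% | 50 / 46 / 4% |

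It agrees to within about 2 points.

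**4. How different would a direction-only rule be?** From the stated table, any result favouring prism is Proceed plus Uncertain:

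- True -0.25: 11 + 62 = 73%, against 11% for Proceed.
- True -0.50: 27 + 62 = 89%, against 27%.
- True -0.75: 50 + 46 = 96%, against 50%.

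At a true difference of 0 (recomputed), direction alone is met 50% of the time and Proceed 2.6%.

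**5. How different would a p<0.05 rule be?** The critical observed difference is −1.67 × SE. At SD 1.5 this is -0.65. Over the protocol's interval for the SD ("95% CI = 1.2 to 1.8 points") it runs from -0.52 to -0.78. At a true -0.75, the chance of p<0.05 compares with the 50.0% chance of Proceed as follows:

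- SD 1.5: 60.4%, so 60.4 − 50.0 = 10.4% of trials would be significant yet Uncertain.
- SD 1.2: 77.3%, so 27.3% would be.
- SD 1.8: 47.7%, so none would be, and 50.0 − 47.7 = 2.3% would reach Proceed without p<0.05.

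**6. Do steps 4 and 5 measure anything the plan does?** They would matter only if the plan adopted direction or significance as its criterion. Set side by side, the texts do not say so:

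- The SAP sentence contrasts a two-sided with a one-sided test. Its word only separates better from better-or-worse. With prism substituted, it fits Protocol 5.2.1, where zero or a difference favouring non-prism means Do not proceed, so only one tail can lead to a full-scale trial.
- SAP section 1 is not a competing basis. It joins the opening of Protocol 1.14 to the preamble of Chapter 5.
- Protocol 5.2.1 sets significance aside explicitly in favour of size.

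**7. Normal scores.** SAP section 2 says only that the transformation would be considered, for a departure from normality that it does not expect. Protocol 5.2.1 states its cut-offs in points of mean control score. An analyst applying the guideline therefore has to use the difference in points.

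**The case for a change.** The strongest argument for a change is that an analysis plan should stand alone on the question the study exists to answer. The sentence sits in the paragraph defending the primary test. The only numerical threshold that the SAP attaches to the primary result is p<0.05, which governs whether p-values are given for the secondary outcomes (SAP section 3). Someone holding only the SAP therefore sees a question about being better and a p-value, although the protocol moved away from significance because power was 61%. Three sentences would put this right at almost no cost.

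Part of this stands. The treatment name is wrong, and the sentence is looser than Protocol 5.2.1. Naming prism and non-prism would be a harmless tidy-up if the SAP were reopened for another reason.

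The rest does not carry. The SAP states that it is based on Protocol version 1.0, and the guideline is in that protocol's statistical chapter. The SAP supplies what the guideline needs, namely the adjusted prism minus non-prism difference in points, and section 4 adds a 95% confidence interval for distance control. The p<0.05 condition concerns secondary p-values and says nothing about proceeding. A fuller rewrite has its own risk: wording that binds the decision to the cut-offs would turn into a rule what the protocol offers as an aid, to be weighed with side effects.

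**Conclusion.** No change to the plan follows. The wrong treatment name is a clerical slip, possibly wording carried over from the group's overminus studies, though the documents do not say so. The missing cross-reference to the guideline, and the unstated scale if normal scores were used, are gaps that any analyst working from both documents fills correctly.

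The effect on planned results is nil: the contrast, ANCOVA, sidedness, intervals and 61% power are unchanged. The large differences between rules (89% against 27% at a true -0.50, or 10% significant but Uncertain at a true -0.75) describe a misreading that Protocol 5.2.1 rules out.

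This rests on two assumptions: that those deciding whether to proceed use the protocol's guideline, as Protocol 5.2.1 intends, and that the sentence is read in its context as a reason for one tail. The probabilities use the unadjusted SD, as the protocol's table does. Baseline adjustment would alter the SE by an amount the documents do not give, but the conclusion does not depend on it.
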